9.8 Unscheduled Visit

A subject who returns to the investigational site between protocol-required follow-up for a clinical event in the target limb is considered to have an Unscheduled Visit. A physical examination and evaluation for SAEs will be completed and recorded on the appropriate CRFs. Angiography and/or duplex ultrasound should be repeated if clinically indicated and/or within the institution's standard of care.

9.9 Data Collection

9.9.1 Source Documents

Data recorded onto paper case report forms (CRF) must be traceable to source documents. Source documentation is defined as the first-time data appears and may include original documents, data, and medical records (e.g., hospital records, clinical and office charts, laboratory notes, etc.).

9.9.2 Deviation Handling

A deviation is any event in which the study is not conducted according to the protocol, applicable laws or regulations or the Investigator Agreement. Deviations may include, but are not limited to the following:

- Failure to obtain informed consent prior to participation
- Incorrect version of the informed consent form used
- Failure to obtain IRB approval before enrolling subjects in the study
- Included subject did not meet inclusion/exclusion criteria
- Required testing and/or measurements not done or incorrectly done
- Subject missing a required follow-up
- Follow-up was completed outside window
- Source data permanently lost
- Enrollment of subjects during lapse of IRB approval

Reporting of all deviations should comply with IRB policies and must be reported to VentureMed as soon as possible upon the site becoming aware of the deviation. All deviations will be documented.

9.9.3 Subject Withdrawal or Discontinuation

Every subject should be encouraged to remain in the study until they have completed the required follow-up per the protocol, however subjects have the right to withdraw their consent to participate at any time during the study. Withdrawal of a subject from the study can also occur at the direction of the Principal Investigator without the subject's consent for any reason.

If a subject expires, has the access site abandoned, withdraws early, or is withdrawn from the study early by the Investigator, the reason for withdrawal must be recorded in the subject's medical record and on the Exit Form.

9.9.4 Loss to Follow-Up

Every attempt should be made to have all subjects complete the follow up schedule. A subject will be considered lost-to-follow-up after three documented unsuccessful attempts to make contact (phone, email, text, or mail). Once deemed lost-to-follow-up, the communication efforts must be recorded in the subject's medical record and on the Exit Form.

10 Risks and Benefits

10.1 Potential Risks

This is a post-market study in which the risks to subjects are no greater as a result of study participation. Potential risks or complications anticipated with the use of the market-released FLEX Vessel Prep System, catheterization procedure, and market-released PTA include, but may not be limited to, those listed in the Instructions for Use of the Test and Control devices.

Subjects will be informed of any significant new findings that develop during the course of the study that may affect their willingness to continue participation. The Investigator will oversee all safety aspects of the study and report all adverse events to the IRB.

10.2 Potential Benefits

There are no guaranteed benefits from participation in the study. It is possible that treatment with the FLEX Vessel Prep System prior to use of PTA may improve and maintain blood flow through the treated AVF, resulting in the need for fewer treatments. This may allow for continued/resumption of AV access for the purpose of hemodialysis. Additionally, it is possible that lower balloon inflation pressures following FLEX Vessel Prep use will result in fewer complications and potentially less pain experienced during the procedure. Information gained from the conduct of this study may be of benefit to other persons with the same medical condition.

11 Serious Adverse Event Assessments

The Investigator is required to assess and document in the medical record all Serious Adverse Events (SAEs) observed in subjects from the time of enrollment until the event resolves or the subject exits the study. In cases in which SAEs are unresolved at the time of study exit, this will be documented on the CRF.

The Investigator is responsible for reporting SAEs to VentureMed as soon as possible, but no later than 10 working days after the Principal Investigator is first aware of the event, by completing the Adverse Event CRF. The Principal Investigator is responsible for reporting the SAE to the IRB as applicable.

12 Statistical Design and Methods

This is a prospective, multicenter, randomized (1:1) study of FLEX Vessel Prep prior to PTA vs PTA alone for the treatment of de novo and non-stented restenotic lesions in the AVF. The study will enroll at up to seven centers in the US.

Comparison of binomial proportions will be performed using Fisher's exact test. Time-to-event analyses using the Kaplan-Meier method may be conducted to supplement the primary analysis of proportions. Comparisons of continuous variables will be performed using a two-sample t-test or Wilcoxon rank-sum test.

For the primary efficacy endpoint and other 6-month endpoints that compare the proportion of subjects between arms, the numerator is the number of subjects with an event within 6 months and the denominator is the number of subjects with an event or who were followed for at least 150 days.

For the primary safety endpoint and other 30-day endpoints that compare the proportion of subjects between arms, the numerator is the number of subjects with an event within 30 days and the denominator is the number of subjects with an event or who were followed for at least 23 days.

The primary analysis will be based on intent-to-treat, including all subjects with available follow-up data analyzed by the arm to which they were randomized. Two-sided p-values less than 5% and one-sided p-values less than 2.5% will be considered statistically significant. For this post-market study, statistically significant differences are not anticipated. The study is intended to provide estimates of the differences between groups. Estimated differences and their 95% confidence intervals will be reported for all endpoints. For the primary efficacy endpoint, if primary patency rates are 60% and 80% in the control and treatment arms respectively, the 95% confidence interval width will be approximately $\pm 25\%$. For the primary safety endpoint, if SAE rates are 5% in both arms, the 95% confidence interval width will be approximately $\pm 17\%$.

Further details on the statistical methods, including justification, timing of interim analysis can be found in the Statistical Analysis Plan.

13 Ethics

The study will be conducted according to the study protocol, Clinical Trial Agreement, and all federal,

regulations, standards, and requirements including: 21 CFR Parts 11, 50, 54, 56, and 45 CFR part 46.

The clinical site will not begin enrolling subjects until the required approval/favorable opinion from the IRB has been obtained.

The site must provide VentureMed with a copy of the investigational site's IRB approval letter and the IRB-approved Informed Consent Form. If applicable, approvals for the continuation of the study must be kept current in accordance with the IRB's review schedule. All site communications to and from the IRB must be forwarded to VentureMed as they are sent/received.

VentureMed will be informed by the IRB and/or the Investigator in case any action is taken by an IRB with respect to this investigation.

This study was publicly registered on www.clinicaltrials.gov prior to first enrollment in accordance with the 2007 Food and Drug Administration Amendments Act (FDAAA).

14 Study Administration

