5.2 Endpoints

5.2.1 Primary Endpoints

Primary endpoints for the study are as follows:

- Primary Efficacy Endpoint: Target Lesion Primary Patency Rate through 6 Months

Defined as freedom from clinically driven target lesion re-intervention (CD-TLR) or access circuit thrombosis measured through 6 months post-procedure.

- Primary Safety Endpoint: Serious Adverse Event Rate within 30 Days

Defined as the Serious Adverse Event (SAE) rate involving the AV access circuit through 30 days post-procedure.

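### Fisher's exact test on 6-month patency is conservative at these arm sizes and costs about 3 to 10 points of power at 60% v 80%; a log-rank or exact unconditional test would recover most of it

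*Combined protocol and SAP*

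**What the plan says.** Section 5.2.1 defines the primary efficacy endpoint as a first-event outcome: "Defined as freedom from clinically driven target lesion re-intervention (CD-TLR) or access circuit thrombosis measured through 6 months post-procedure". Section 12 analyses it as a 6-month proportion. On the test it says: "Comparison of binomial proportions will be performed using Fisher's exact test". On who is counted, it says that "the denominator is the number of subjects with an event or who were followed for at least 150 days". Survival methods are a possible addition: "Time-to-event analyses using the Kaplan-Meier method may be conducted to supplement the primary analysis of proportions". No between-arm time-to-event test is named there.

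On significance, Section 12 states: "Two-sided p-values less than 5% and one-sided p-values less than 2.5% will be considered statistically significant". The same paragraph says that significant differences are not expected, that the aim is to estimate differences, and that 95% CIs will be reported for all endpoints. Its planning case for efficacy is "if primary patency rates are 60% and 80% in the control and treatment arms respectively". It states no power. Further methods are referred to a Statistical Analysis Plan; no separate text of that plan is in the document reviewed.

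**The concern.** Fisher's test holds its error rate at or below 5% by conditioning on the total number of events. In small trials this leaves its true error rate well below 5%, and power is lost with it. The endpoint is a time to first event and a survival analysis is already foreseen, so a test that uses the full 5% is available at no extra cost in data.

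Although the plan plays down significance, it sets a 5% threshold, and the primary p-value will be read against it. A true 20-point patency gain would be reported as not significant somewhat more often than necessary.

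**Working it through.** **Inputs.** Patency 60% control and 80% test, and two-sided 5% (Section 12); up to 75 subjects (Section 3), randomised 1:1 (Section 9.5), so 37/38 or 38/37 at the maximum. Assumed, because the documents do not say: hazard shape, exit rate and final arm sizes.

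**The plan's own figure.** Section 12 gives a precision of about ±25 points for efficacy, not a power. The Wald half-width at 37/38 is 1.96 × √(0.6×0.4/37 + 0.8×0.2/38) = 1.96 × 0.1034 = 0.203, or about ±20 points. At 25 per arm it is 1.96 × √(0.24/25 + 0.16/25) = 0.248. The stated figure therefore fits about 25 per arm better than 37 or 38. That is a separate matter and does not enter the power comparison.

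**True size of Fisher's test.** Sum the two binomial probabilities over all tables with p < 0.05, at a common patency of 0.6, 0.7 and 0.8:
- 37/38: 3.6% to 3.9%
- 34/34: 2.4% to 3.0%

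The simulated log-rank size was 4.8% to 5.0%.

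**Power at 60% v 80%, no early exits.** Fisher and the uncorrected chi-square are by exact enumeration of both binomials. The log-rank is simulated with constant hazards and censoring at day 180. The hazard ratio is ln 0.8 / ln 0.6 = 0.437.

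| Control/test | Fisher | Chi-square, same yes/no data | Log-rank | Log-rank minus Fisher |
|---|---|---|---|---|
| 37/38 | 45% | 48.5% | 48% | 3 |
| 38/37 | 42% | 47.2% | 48% | 6 |
| 37/37 | 38% | 47.5% | 47% | 9 |
| 36/38 | 42% | 46.4% | 48% | 6 |
| 36/36 | 37% | 47.1% | 47% | 10 |
| 35/35 | 36% | 45.3% | 45% | 9 |

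Check on the log-rank column: expected events at 37/38 are 37×0.4 + 38×0.2 = 22.4. Schoenfeld's formula gives power Φ(√(22.4/4) × |ln 0.437| − 1.96) = Φ(2.366×0.828 − 1.96) = Φ(0.00) = 50%, close to the simulated 48%.

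**Where the loss comes from.** The chi-square uses the same yes/no data as Fisher and is within about 2 points of the log-rank in every row. Dichotomising at 6 months therefore costs about 0 to 2 points here; the rest is Fisher's conservatism.

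**Early exits.** The documents give no rate. At 37/38 with assumed random exit of 5%, 10% and 20%, and Fisher applied under the plan's 150-day rule, Fisher v log-rank is 41.1% v 46.8%, 40.2% v 46.4% and 37.1% v 44.5%. The gaps are 5.7, 6.2 and 7.4 points.

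**Hazard shape.** With 6-month patency held at 60% v 80% and no exits:
- No effect for the first 30 days, 37/38: log-rank about 45%, Fisher 45%; gain about zero.
- No effect for the first 60 days, 37/38: log-rank about 41%, Fisher 45%; a loss of about 4 points. At most other splits the log-rank is level or slightly better.
- Mainly early effect (all of it in the first 120 or 150 days; N = 75, averaged over small imbalances, 0% or 10% exit): gain of about 8 to 13 points.

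**The case against.** The strongest reply is that Section 12 disclaims significance, claims no power and promises estimates with 95% CIs. Both tests have less than 50% power at 60% v 80%, so a true 20-point gain would more likely than not miss the 5% threshold either way. This stands, and it limits the point to a modest improvement. It does not justify the weaker test, since the threshold remains in the plan.

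A reader might infer that the plan wastes its data by reducing event times to yes/no. The calculations do not support that: at the plan's rates a chi-square on the same yes/no data matches the log-rank. A reader might also infer a dependable log-rank gain. That needs roughly proportional hazards or an early effect, and the documents give no hazard shape. Gains of 9 to 10 points need exactly equal arms, where Fisher does worst.

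It would also go too far to say that time-to-event analysis is absent. It is foreseen as an option, and the separate Statistical Analysis Plan may say more. If that plan already names a between-arm survival test, only the ranking of the two analyses is left to settle.

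Two practical objections stand. Section 3 records enrolment as completed in April 2022 and the text describes no blinding, so a change of test needs a dated justification. Section 9.7 withdraws subjects whose access is abandoned, and censoring them at exit may be informative.

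**Conclusion.** The point holds as a modest one about choice of test. At the plan's 60% v 80%, Fisher's exact test gives about 36% to 45% power with 35 to 38 per arm, against about 45% to 48% for a log-rank test under proportional hazards: a loss of about 3 to 10 points, or 3 to 6 at 37/38 and 38/37 with no exits. Nearly all of it reflects a true size of about 2.4% to 3.9% in place of 5%.

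The Fisher figures are exact given the arm sizes and rates. The log-rank advantage rests on hazard shape and on exits unrelated to patency, neither of which the documents establish. The documents do not support a reading that the primary result is invalid, or that the choice of test decides whether the study succeeds.

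**What to change.** In Section 12 and the Statistical Analysis Plan, before any between-arm comparison is seen, take one of two routes for target lesion primary patency:

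1. Name a two-sided log-rank test of time from index procedure to first CD-TLR or access circuit thrombosis, through day 180, with event-free subjects censored at exit or day 180.
2. If the 6-month proportion is to stay the test scale, replace Fisher's test with a less conservative exact unconditional test such as Boschloo's. This addresses the main cause directly and does not depend on hazard shape.

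Under either route, keep the 6-month patency difference with its 95% CI as the main reported estimate and Fisher's test as supportive.

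The cost is wording and a dated justification; no visits or subjects are added. Event and exit timing is already needed for the 6-month and 150-day rules. Section 9.7 lists reintervention information without expressly requiring dates, so confirm that the case report forms capture them.

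State the downsides of route 1: it tests the whole curve rather than the 6-month point and loses its advantage under a delayed effect; any hazard ratio assumes roughly proportional hazards; and censoring at exit assumes that exits are unrelated to patency, which withdrawal for access abandonment may violate. If between-arm results have already been seen, leave Fisher's test as the planned comparison and report the alternative as supplementary.

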9.1 Schedule of Events

Table1 provides an overview of the assessment requirements for the study.

Table 1: Study Assessment Requirements

Assessment/Procedure	Baseline/Screening (within 30 days of procedure)	Index Procedure	Discharge (within 7 days post-procedure)	30 Days (± 7 days)	3 Months (90 ± 15 days)	6 Months (180 ± 30 days)	Unscheduled Visit	Target AVF Abandonment
Informed Consent	X							
Medical History	X							
Physical Exam	X						X	
Medication Assessment	X	X	X					
Numeric Rating Scale	X	X						
Angiography		X					X*	
Randomization		X						
Serious Adverse Event Collection		X	X	X	X	X	X	X
Abandonment of Fistula								X

* Collect if revascularization required.

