9.7 Follow-up Requirements

The subject will be followed after 30 days, 3 months and 6 months post procedure.

The following assessments will be performed during these follow-ups:

- Evaluation for SAE's
- Patency of Access Site
- Access Circuit Reintervention Information

If the access site used in the study is abandoned, the subject should be withdrawn from the study.

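### The 6-month denominator keeps every failure but drops event-free subjects who exit before day 150, and abandonment without a counted event has no failure rule; Kaplan-Meier and one abandonment sensitivity analysis should be required beside the primary proportion

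*Combined protocol and SAP*

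**What the plan says.** Protocol section 12 compares proportions. For the 6-month endpoints, failures up to month 6 form the numerator. Of the other half of the fraction the section says: "the denominator is the number of subjects with an event or who were followed for at least 150 days". The time-to-event analysis is optional: "Time-to-event analyses using the Kaplan-Meier method may be conducted to supplement the primary analysis of proportions".

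Section 5.2.1 gives the primary efficacy endpoint: "Defined as freedom from clinically driven target lesion re-intervention (CD-TLR) or access circuit thrombosis measured through 6 months post-procedure". Abandonment of the fistula is not a component. Section 9.7 says: "If the access site used in the study is abandoned, the subject should be withdrawn from the study". Section 9.9.3 requires the reason for exit on the Exit Form; its list begins "If a subject expires, has the access site abandoned, withdraws early, or is withdrawn from the study early by the Investigator". Table 1 in section 9.1 has a row "Abandonment of Fistula" and an abandonment column in which SAEs are also collected. The same table sets the 6-month visit at 180 ± 30 days, so day 150 is the lower edge of that window.

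Section 12 describes the primary analysis as intent-to-treat but limits it to subjects with available follow-up. It also states the aim: "The study is intended to provide estimates of the differences between groups". It refers to a separate SAP for further statistical detail. That SAP was not in the text reviewed.

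**The concern.** Take two subjects. One has a clinically driven re-intervention on day 40 and leaves; this subject is counted. The other is event-free and leaves on day 140; this subject is not. Selection on outcome pulls each arm's patency down. If the arms lose subjects at different rates, it also distorts their difference, and that difference is what the study sets out to estimate.

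The second gap is abandonment. Abandonment after a counted thrombosis or CD-TLR is already an event and is not affected. A fistula abandoned without one leads to withdrawal under section 9.7. Before day 150 the subject then leaves the denominator. From day 150 on, the subject counts as patent. Some of these abandonments may be access failures. In arms of about 37, a few of them on one side would matter.

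**Working it through.** **Inputs.** Patency of 60% (control) and 80% (test), and the ±25% half-width: section 12. Up to 75 subjects, 1:1, so 37 and 38: section 3. Day 150: section 12. The documents give no exit or abandonment rate, so all such rates below are assumptions.

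**The plan's precision figure.** A Wald half-width at 37/38 is 1.96 × √(0.6×0.4/37 + 0.8×0.2/38) = 20.3 points. With 25 per arm it is 1.96 × √(0.24/25 + 0.16/25) = 24.8. The plan states neither the number nor the method behind ±25%, and 75 is a maximum, so this shows no error. The figure serves here only as a yardstick.

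**The denominator rule.** Assume exponential event times with hazard λ = −ln(S)/180, where S is event-free probability at day 180. Assume exponential exits unrelated to outcome with hazard μ = −ln(1−e)/150, where e is the exit probability by day 150. If 6-month visits fall on days 180–210:

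- observed events E = λ/(λ+μ) × [1 − exp(−180(λ+μ))]
- retained subjects D = λ/(λ+μ) × [1 − exp(−150(λ+μ))] + exp(−150(λ+μ))
- patency by the rule = 1 − E/D

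Example, control with e = 25%: λ = 0.5108/180 = 0.002838, μ = 0.2877/150 = 0.001918, E = 0.5967 × 0.5752 = 0.3432, D = 0.5967 × 0.5100 + 0.4900 = 0.7943. Patency = 1 − 0.3432/0.7943 = 56.8%, against a true 60%. At e = 15% it is 58.2%. For the test arm the rule gives 78.9% at 15% and 77.9% at 25%, against 80%. The understatement is 1.1 to 3.2 points.

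If visits are spread evenly over days 150–210, an event at day t between 150 and 180 is seen only with probability (210−t)/60, about three quarters on average. With no exits at all, control misses about a quarter of the 65.3 − 60.0 = 5.3 points of events in that month, and test about a quarter of 83.0 − 80.0 = 3.0. The rule then gives 61.3 and 80.7, a difference of 19.4. Visit timing alone moves the estimate.

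Difference by the rule, in points (true value 20.0):

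| Exits by day 150, control/test | Visits days 180–210 | Visits days 150–210 |
|---|---|---|
| 0% / 0% | 20.0 | 19.4 |
| 15% / 15% | 20.6 | 20.1 |
| 25% / 25% | 21.1 | 20.6 |
| 5% / 25% | 18.5 | 17.9 |
| 25% / 5% | 22.9 | 22.4 |

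Measured from the no-exit row of the same column, the 5% versus 25% gap moves the difference by −1.5 or +2.9 (days 180–210) and by −1.6 or +3.0 (days 150–210). Kaplan-Meier at day 180, simulated with 2,000,000 subjects per arm under the same assumptions, gives 19.9 to 20.0 for the unequal exits.

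**Abandonment.** Take 15 failures of 37 in control and 8 of 38 in test: 22/37 = 59.5% and 30/38 = 78.9%, difference 19.5. Let three event-free fistulas be abandoned, all in one arm.

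- All in control. Scored patent: 19.5. Dropped: 30/38 − 19/34 = 23.1. Failed: 30/38 − 19/37 = 27.6.
- All in test. Scored patent: 19.5. Dropped: 27/35 − 22/37 = 17.7. Failed: 27/38 − 22/37 = 11.6.
- Two in each arm. Dropped: 28/36 − 20/35 = 20.6. Failed: 28/38 − 20/37 = 19.6.

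One-sided cases matter; balanced ones hardly do. Kaplan-Meier does not repair this, because it would censor the abandoned fistula as if it carried the same later risk as those still in use.

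**The case against.** The strongest reply is about size. Even a 20-point gap in exits, which nothing in the documents suggests, moves the difference by no more than about 3 points against a stated ±25%. Section 12 does not anticipate significant differences, so no confirmatory decision hangs on this. That stands, and it is why the proportion can remain primary.

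Kaplan-Meier is no cure-all either. If last contacts cluster at days 150–165 with 15% exits, simulation gives about 63 and 81.5 by Kaplan-Meier and about 62 and 81 by the rule. The standard deviation of the difference is 12.0 against 10.9. In that case it gains nothing. This also stands.

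Abandonment without a counted event may be rare. Section 8.3 excludes anticipated conversion to peritoneal dialysis and planned surgical revision, and section 8.2 requires a life expectancy of at least 12 months. The three one-sided cases are illustrative, not expected.

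A reader might infer that the plan would hide abandonment altogether. It would not: Table 1 requires SAE collection at abandonment, section 5.2.2 includes access-circuit SAEs through 6 months, and the Exit Form records the reason. These are partial safeguards, since an abandonment need not be an SAE. A reader might also take the move from 19.5 to 27.6 as bias in the stated endpoint. It is not: counting abandonment as failure is a broader endpoint than section 5.2.1 defines.

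**Conclusion.** The concern holds as a modest weakness in the analysis rules. The 6-month denominator selects on outcome. Under exits unrelated to outcome and 60%/80% patency, this costs about 1 to 3 points of patency per arm at 15–25% exits with visits on days 180–210. It moves the difference by about 1 point or less with balanced exits, and by about 1.5 to 3 points at 5% versus 25%. Visit timing accounts for part of any shift when visits spread over days 150–210. The documents do not support the stronger reading that the 6-month comparison is seriously biased.

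Abandonment without a counted event is the larger uncertainty. Its effect can go either way and depends on how many cases fall in one arm, which the documents do not let anyone predict. Nor can it be said that the SAP lacks rules for this; the finding is only that the reviewed text does not require them.

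**What to change.** Keep the section 12 proportion as primary, and say so. Then:

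- (a) Make the Kaplan-Meier analysis required instead of optional: the difference in event-free probability at day 180 with a 95% confidence interval, in all randomized subjects, censored at last contact, reported beside the proportion.
- (b) Add one sensitivity analysis that counts abandonment of the target AVF as failure. Label it a broader endpoint than section 5.2.1, not a bias correction.
- (c) Report the number excluded from the 6-month denominator in each arm by reason: death, abandonment, withdrawal, loss to follow-up.

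The cost is a little analysis work and no new data: Kaplan-Meier is already named, Table 1 collects abandonment, and the Exit Form records reasons. Kaplan-Meier assumes non-informative censoring. Its precision is otherwise close to the rule's (simulated standard deviation of the difference 11.3 against 11.2 at 5%/25% exits, and 11.5 against 11.2 at 25%/5%). Section 3 gives enrollment as complete in April 2022 with close-out planned for about October 2022. The additions should therefore be dated before outcomes by arm are seen, or labelled post hoc if they have been. If the SAP cited in section 12 already requires these analyses, a cross-reference is enough.
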